8.5.2. Analysis of secondary objectives

These analyses will be conducted only among ART-experienced new users of RPV, RAL, EVG/c, BIC, DRV(/r/c), or DTG who were virologically suppressed at the time of switch to a core agent of interest (stable switch). Using data from the most recent visit in the 12-month baseline period preceding the index date of core initiation, patients with a HIV-1 RNA viral load measurement < 200 copies/mL will be considered suppressed.

Baseline demographic and clinical characteristics

All baseline outcomes and covariates listed in sections 8.3.2. and 8.3.3. will be summarized for patients who have achieved virologic suppression (<200 copies/mL) prior to switch to RPV, RAL, EVG/c, DRV(/r/c), BIC, or DTG between 01AUG2013 and 31DEC2017; medians and interquartile ranges for continuous variables and counts and percentages for categorical variables will be provided.

Description of follow-up levels of total cholesterol, HDL, LDL, triglycerides, weight and BMI

Total cholesterol, HDL, LDL, triglycerides, weight, and BMI will be assessed continuously at 6,12, and 24 months after initiation. BMI and lipids will also be assessed categorically, as the proportion of patients in each BMI and lipid category and the proportion of patients changing categories of BMI among patients initiating each core agent of interest (see section 8.3.2 for a definition of changes in categories).

8.5.3. Study size considerations

The sample size required to detect a range of differences in mean BMI with 80% power for the adjusted linear regression looking at the association between specific core agent initiation and continuous BMI has been estimated under the following assumptions [35]:

• Number of predictors:

The exposure of interest is a 5-level categorical variable, which is equivalent to 4 factor variables, thus requiring 4 degrees of freedom. Calculations were performed assuming a total of 10 covariates included in the model in addition to the exposure variables.

• Effect and variability:

Partial correlations ranging from 0.02 to 0.20 were assumed, corresponding to detectable differences in mean BMI ranging from 0.04 to 0.41. The equivalence between partial correlation and difference in mean BMI was calculated as:

$$\rho = \frac{d}{\sqrt{d^2 + 4}}$$

where ρ = partial correlation and d = difference in mean BMI

The sample sizes required to detect effect sizes ranging from ρ =0.02 to ρ =0.20 with 80% power are presented numerically with corresponding differences in mean BMI (Table 2). They are also presented graphically across a range of partial correlations in Figure 2, along with the estimated sample size available in each stratum of baseline BMI in OPERA, based on the following assumption:

[figure not shown]
 Estimated sample size in OPERA, stratified by baseline BMI category: As of August 17, 2018, there were 91,415 HIV+ patients in OPERA, among whom 17,370 were ART-experienced, had a baseline BMI and initiated one of the core agents of interest for the first time between August 01, 2013 and December 31, 2017. Of these, 510 patients were underweight, 6,598 were normal weight, 6,298 were overweight, and 3,964 were obese at baseline.

0 , ,			C .
Power	Correlation Factor	Difference in Mean BMI	Sample Size Required*
0.80	0.02	0.04	29832
0.80	0.04	0.08	7453
0.80	0.06	0.12	3309
0.80	0.08	0.16	1858
0.80	0.10	0.20	1187
0.80	0.12	0.24	822
0.80	0.14	0.28	602
0.80	0.16	0.32	460
0.80	0.18	0.37	362
0.80	0.20	0.41	292

Table 2. Required sample size for the multivariate linear regression of BMI on core agent, by correlation factor and difference in mean BMI, assuming 80% power

*The estimated sample sizes for each BMI stratum are 510 patients classified as underweight; 6,598 classified as normal weight; 6,298 classified as overweight; and 3,964 classified as obese

Figure 2. Sample size required and available for the multivariate linear regression of BMI on core agent, by correlation factor

These estimates of sample size required to detect a range of differences in mean BMI are likely a overestimation of the sample size required when inverse probability of censoring weights are included. However, given the use of a continuous outcome, the minimal detectable difference in mean BMI remains small even with sample sizes much smaller than the estimated sample size available in OPERA. For example, only 292 patients are required to detect a difference of 0.4 units in BMI; the smallest stratum available in OPERA is the underweight group, with 510 patients.

The method employed here is considered appropriate when calculating sample sizes for a multiple regression analysis with continuous or categorical predictors, and a continuous outcome [35, 36]. Our approach is based on partial correlations, but an alternative is based on the proportion of variation explained by the model (R²) [37]. However, the R² approach requires knowledge of the expected R² values for the full and reduced models (or the difference between them) based on previous research. The R² approach seemed less appropriate in this setting due to the lack of published data on the relationship between the core agents of interest in this study and BMI. Another method is to perform sample size calculations based on the one-way analysis of variance (ANOVA) [38]. One important limitation of this approach is that the influence of additional covariates in the model are not accounted for in these power calculations which assumes one degree of freedom. Another limitation of the one-way ANOVA approach is that it requires making some assumptions about the data that may not be appropriate, such as the mean BMI for each of the five exposure groups and the overall standard deviation [38].

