6.2. Rationale

Disentangling weight gain due to improved health status from weight gain due to an undesired effect of therapy requires an assessment of a large number of patients who may be progressing toward a stable health status or in whom a stable health status has been achieved and maintained.

Following raised disproportionality analysis (DPA) scores for both DTG and DTG/ABC/3TC detected through the routine pharmacovigilance, clinical trial data, spontaneous case reports, and published studies were reviewed. The cumulative evidence could not rule out an association between DTG exposure and weight gain, leading to a recommendation for a label change indicating weight gain as an uncommon ADR. This analysis, utilizing data from a large real-world population of treated HIV patients, will provide additional information to support the signal evaluation.

7. **RESEARCH QUESTION AND OBJECTIVE(S)**

Primary:

- Among new users of DTG, RPV, RAL, BIC*, EVG/c and DRV(/r/c): To describe BMI categories, weight, lipid levels (e.g. total cholesterol, HDL, LDL, triglycerides), and lipodystrophy at core agent initiation and at 6,12, and 24 months after core agent initiation, stratified by ART- naïve and ARTexperienced.
- Among ART-experienced new users of DTG vs. RPV, RAL, BIC*, EVG/c or DRV (/r/c): To estimate the association between specific core agent initiation and changes in BMI at 6, 12, and 24 months after core agent initiation.

Secondary:

 Among ART-experienced patients who were suppressed at switch (stable switch) to DTG, RPV, RAL, BIC*, EVG/c, or DRV(/r/c): To describe BMI categories, weight, and lipid panels levels (e.g. total cholesterol, HDL, LDL) at core agent initiation, and at 6,12, and 24 months after core agent initiation

*Due to recent approval and more limited potential follow-up, patients taking BIC will be included for 6-month outcomes only.

8. **RESEARCH METHODS**

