8.3. Variables

8.3.1. Exposure definitions

Exposures

• First exposure to any core agent of interest (DTG vs. RPV, RAL, BIC, EVG/c or DRV(/r/c)), after inclusion in the OPERA database. Prior exposure to other core agents of interest is not allowed after inclusion in the OPERA database.

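### Table 2 is sized for five core agents, but the 6-month regression has six, so the overall test at 6 months needs about 7.5% more patients than stated

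*Protocol*

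**What the plan says.** Section 8.5.3 introduces its calculation as follows: "The sample size required to detect a range of differences in mean BMI with 80% power for the adjusted linear regression". It names no time point. The exposure is then fixed: "The exposure of interest is a 5-level categorical variable, which is equivalent to 4 factor variables, thus requiring 4 degrees of freedom". The remaining predictors are fixed as well: "Calculations were performed assuming a total of 10 covariates included in the model in addition to the exposure variables". That makes 4 + 10 = 14 predictors. The effect sizes are partial correlations: "Partial correlations ranging from 0.02 to 0.20 were assumed, corresponding to detectable differences in mean BMI ranging from 0.04 to 0.41". The text after Figure 2 gives the worked example, "only 292 patients are required to detect a difference of 0.4 units in BMI", and compares it with the underweight stratum of 510. When that text discusses a one-way ANOVA alternative, it again counts five exposure groups.

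Two other places count six agents. The second primary objective in section 7 begins "Among ART-experienced new users of DTG vs. RPV, RAL, BIC*, EVG/c or DRV (/r/c", and the asterisk leads to a footnote that restricts BIC to the 6-month outcomes. Section 8.3.1 defines the exposure as "First exposure to any core agent of interest (DTG vs. RPV, RAL, BIC, EVG/c or DRV(/r/c", again DTG plus five others. Section 8.5.1 applies the adjusted linear regression to BMI change at 6, 12 and 24 months.

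**The concern.** Read together, these sections give two exposure variables. At 12 and 24 months BIC drops out, leaving five levels and 4 degrees of freedom, as section 8.5.3 assumes. At 6 months BIC is in, giving six levels, 5 degrees of freedom and 15 predictors. Section 8.5.3 presents one calculation for the regression as a whole and has no separate 6-month figure, so its premise is wrong for one of the three primary association models.

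Table 2 is the protocol's only quantified statement of what the association analysis can detect. A reader who applies it at 6 months will credit the six-agent comparison with slightly more power than it has. A programmer who takes the number of levels from 8.5.3 could also build the 6-month model with the wrong set of agents.

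**Working it through.** **Inputs**
- Power 80%; 10 covariates besides the exposure; ρ from 0.02 to 0.20 (section 8.5.3).
- Exposure degrees of freedom u: 4 as stated in 8.5.3; 5 for the six agents in sections 7 and 8.3.1.
- Alpha 0.05 for the overall test of core agent. This is an assumption, because section 8.5.3 gives no alpha. The exact match below supports it.

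**Formulas** (partial F test in multiple regression, fixed predictors)
- Effect size: f² = ρ² / (1 − ρ²)
- Noncentrality: λ = N × f²
- Degrees of freedom: u in the numerator and N − u − 10 − 1 in the denominator
- Required N: the smallest N for which noncentral-F power is at least 0.80

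**Step 1: reproduce the plan's figure.** At ρ = 0.20, f² = 0.04 / 0.96 = 0.04167. With u = 4 and N = 292, λ = 12.17, the denominator has 292 − 4 − 10 − 1 = 277 degrees of freedom, and power is 80.1%. At N = 291 power is 79.9%. So 292 is reproduced, as are the other nine rows. Setting u = 1 instead gives 191, so the table was built for a 4-degree-of-freedom overall test.

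**Step 2: change only u.** At ρ = 0.20 with u = 5 and N = 292, the denominator has 276 degrees of freedom and power is 76.6%. At N = 313 power is 79.9%. At N = 314, λ = 13.08, the denominator has 298 degrees of freedom and power is 80.1%. The required N is 314.

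**Step 3: all rows.**

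| ρ | Table 2 (4 df, reproduced) | 5 df | Increase |
|---|---|---|---|
| 0.02 | 29,832 | 32,062 | 7.5% |
| 0.04 | 7,453 | 8,010 | 7.5% |
| 0.06 | 3,309 | 3,556 | 7.5% |
| 0.08 | 1,858 | 1,998 | 7.5% |
| 0.10 | 1,187 | 1,276 | 7.5% |
| 0.12 | 822 | 884 | 7.5% |
| 0.14 | 602 | 648 | 7.6% |
| 0.16 | 460 | 494 | 7.4% |
| 0.18 | 362 | 389 | 7.5% |
| 0.20 | 292 | 314 | 7.5% |

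The percentage is the increase over the stated N. As a share of the 5-df requirement the shortfall is about 7.0% (1 − 292/314 = 7.0%). Power of the 5-df test at the stated N is 76.5% to 76.6% in every row.

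**Step 4: effect on the strata.** On the protocol's d scale, d = 2ρ / √(1 − ρ²), the smallest detectable difference in the underweight stratum (510) moves from 0.307 to 0.319. In the obese stratum (3,964) it moves from 0.110 to 0.114.

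**The case against.** The strongest reply is that nothing depends on the difference. Table 2 sets no enrolment target, the sample is whatever the database holds, and 510 exceeds 314. That is correct. A reader might infer that the 6-month analysis is underpowered, and the protocol's figures do not support that.

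Second, objective 2 sets DTG against each other agent, and the 7.5% belongs to the overall test. For a single 1-df contrast at fixed ρ, the required N is the same with 14 or 15 predictors: 191 at ρ = 0.20 and 779 at ρ = 0.10. This also stands. It would be wrong to say that each DTG-versus-comparator contrast needs 7.5% more patients. But Table 2 reproduces only as an overall test, so that is the test whose figures need correcting.

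Third, the conversion from ρ to BMI units treats the standard deviation of BMI change as 1. If the ± values that the background section gives for a cohort of treatment-experienced patients at 6 months are standard errors, the implied standard deviations run from 0.07 × √148 = 0.85 to 0.07 × √382 = 1.37. At a fixed difference in BMI units, N would then change by a factor of about 0.73 to 1.87, far more than 7.5%. This limits how literally 314 can be read as the N for 0.4 BMI units. It does not remove the inconsistency, which holds at every fixed ρ.

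Fourth, Table 2 may have been meant for 12 and 24 months only. Section 8.5.3 does not say so, and the fix would put that on record.

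Finally, a reader might infer that the protocol leaves BIC's place in the model undecided. The footnote to section 7 places BIC at 6 months; section 8.5.3 is the part that is out of step.

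**Conclusion.** The inconsistency is real and limited to the 6-month model. Section 8.5.3 counts five exposure levels where objective 2 and section 8.3.1, with the BIC footnote, give six at 6 months. For the overall F test of core agent, the stated sample sizes need to rise by 7.4% to 7.6%; left as they are, they give about 76.6% power. Table 2 needs no correction on this ground for 12 and 24 months.

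These figures assume alpha 0.05, the protocol's 10 covariates and unchanged ρ. The feasibility conclusion survives on the protocol's own comparison of 510 with the required N. That stratum counts patients with a baseline BMI who started a core agent, whereas section 8.5 keeps only those followed to the time point. The 6-month model would need 314/510 = 61.6% of the stratum in the analysis, against 292/510 = 57.3% under the stated figure. The point is a cheap correction to a stated figure for a primary analysis, not a threat to the study.

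**What to change.** In section 8.5.3, label the present Table 2 and the 292-patient example as applying to the 12- and 24-month models (five levels, 4 df, 14 predictors). Add a 6-month column for six levels, 5 df and 15 predictors, with the values 32,062, 8,010, 3,556, 1,998, 1,276, 884, 648, 494, 389 and 314. State the alpha, and say that all figures refer to the overall test of core agent. Limit the later mention of five exposure groups in the same way.

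If BIC is not meant to be in the 6-month regression, remove it from objective 2 only, in section 7 and in the matching abstract text. Keep it in section 8.3.1: that definition serves the whole study, and the descriptive primary objective and the secondary objective both include BIC.

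The cost is one rerun of the power calculation and a few lines of editing. The 6-month figures become slightly less favourable, and neither the data nor the design changes.

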To our knowledge, four recent studies have reported on weight or BMI increases associated with specific core agents [27-30]. One cohort study included 462 European patients on DTG for more than six months and observed a significant increase in weight (mean increase: 3 kg) and BMI (mean increase: 1 kg/m²) over follow-up; 20% of the patients experienced >10% increase in weight [28]. However, the follow-up timepoints varied between patients and the study did not include a comparison group. Another cohort study following 495 patients virologically suppressed on EFV/tenofovir disoproxil fumarate (TDF)/emtricitabine (FTC) from the Vanderbilt Comprehensive Care Clinic found that weight change over an 18-month period was highest among patients

switching to an INSTI-containing regimen (2.9 kg) when compared to switching to a PIcontaining regimen (0.7 kg) or continuation with EFV/TDF/FTC (0.9 kg) [27]. The greatest change was observed for patients switching to DTG/abacavir (ABC)/lamivudine (3TC) specifically (5.3 kg) [27]. In the SCOLTA cohort, mean BMI increases were estimated among ART-experienced patients at 6 and 12 months following initiation of a new core agent [29]. Mean BMI increase with DTG (n=225) was 0.18 \pm 0.08 at 6 months and 0.30 \pm 0.10 at 12 months. With RAL (n=382), mean BMI increase was 0.17 \pm 0.07 at 6 months and 0.24 \pm 0.08 at 12 months. With EVG (n=148), mean BMI increase was 0.21 \pm 0.07 at 6 months and 0.23 \pm 0.10 at 12 months. With DRV (n=145), mean BMI increase was 0.32 \pm 0.09 at 6 months and 0.41 \pm 0.10 at 12 months. With RPV (n=218), mean BMI increase was 0.06 \pm 0.07 at 6 months and 0.06 \pm 0.08 at 12 months [29]. Although small, BMI increases from baseline were statistically significant (p<0.05) for all core agents assessed at both 6 and 12 months with the exception of RPV (6 months: p=0.39, 12 months: p=0.51) [29].

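### Table 2 labels a two-group standardised difference as BMI units and pairs it with 4-df sample sizes, so the 292-patient figure does not establish 80% power for the DTG-versus-comparator contrasts

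*Protocol*

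**What the plan says.** Section 8.5.3 of the protocol sizes the adjusted linear regression for 80% power. The exposure has five levels, "which is equivalent to 4 factor variables, thus requiring 4 degrees of freedom", and ten further covariates are assumed. Partial correlations from 0.02 to 0.20 are taken as "corresponding to detectable differences in mean BMI ranging from 0.04 to 0.41", using ρ = d/√(d²+4), "where ρ = partial correlation and d = difference in mean BMI". No standard deviation is given.

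Table 2 lists ten sample sizes, from 29,832 at ρ = 0.02 down to 292 at ρ = 0.20. The text then reassures the reader that "only 292 patients are required to detect a difference of 0.4 units in BMI", and sets this against the smallest baseline-BMI stratum, underweight, with 510 patients.

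The second primary objective (section 7) compares DTG with each of the other agents. Section 8.5.1 stratifies that analysis by baseline BMI category.

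**The concern.** Two things do not fit together.

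- **Units.** The conversion formula contains no SD. It links a correlation to a difference in SD units between two groups of equal size. Reading d as BMI units sets the residual SD to 1 without saying so.
- **Test.** The sample sizes are for one joint test of all agent terms. The d column describes one two-group contrast. A multiple partial correlation on 4 df does not translate into a pairwise mean difference through this formula.

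At stake is how a null result in a small stratum will be read. The study is meant to support evaluation of a weight-gain signal. A reader who accepts the 292 figure would take a null DTG contrast among underweight patients as adequately powered for 0.4 BMI units.

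**Working it through.** **Inputs.** Power 80%, 4 tested df, 10 other covariates, ρ from 0.02 to 0.20, and stratum sizes 510, 6,598, 6,298 and 3,964 (all section 8.5.3). Alpha is not stated; 0.05 two-sided is assumed. Agent shares are not stated; five equal groups are assumed unless noted.

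**1. Reproducing Table 2.** Noncentral F with λ = Nρ²/(1−ρ²), numerator df 4, denominator df N−15 and alpha 0.05 gives 29832, 7453, 3309, 1858, 1187, 822, 602, 460, 362 and 292. All ten rows match. A 1-df test at ρ = 0.20 would need 191. The sample sizes are therefore those of the omnibus test.

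**2. The difference column.** Solving the formula gives d = 2ρ/√(1−ρ²). At ρ = 0.20 this is 0.40/√0.96 = 0.408, printed as 0.41. No SD enters.

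On 4 df with five equal groups, ρ = 0.20 means f² = 0.04/0.96 = 0.0417. If only DTG differs from the rest, that is √(0.0417/0.16) = 0.51 SD, not 0.41.

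**3. A plausible SD.** Section 6.1 gives n and ± values by agent for one cohort of ART-experienced patients. Read as standard errors, SD = SE × √n:

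| Agent (n) | 6 months | 12 months |
|---|---|---|
| DTG (225) | 1.20 | 1.50 |
| RAL (382) | 1.37 | 1.56 |
| EVG (148) | 0.85 | 1.22 |
| DRV (145) | 1.08 | 1.20 |
| RPV (218) | 1.03 | 1.18 |
| Pooled | 1.18 | 1.39 |

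Check of the SE reading: RPV at 6 months, 0.06/0.07, gives p = 0.39, as printed. At 12 months, 0.06/0.08 gives 0.45 against a printed 0.51. Rounding can explain the gap, since 0.055/0.085 gives 0.52.

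**4. Power for one DTG contrast of 0.41.** Two-sided t test on N−15 df, noncentrality 0.41/(SD × √(2/n)), with n = N/5. For N = 292, n = 58.4 and √(2/n) = 0.185. For N = 510, n = 102 and √(2/n) = 0.140. The detectable difference is 2.80 × SD × √(2/n).

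| | SD 1.0 | SD 1.2 | SD 1.4 |
|---|---|---|---|
| Power, N = 292 | 60% | 45% | 35% |
| Power, N = 510 (underweight) | 83% | 68% | 55% |
| Detectable difference, N = 510 | 0.39 | 0.47 | 0.55 |
| Total N for 80%, five equal groups | 470 | 675 | 920 |

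The last row is five times 2 × (2.80 × SD/0.41)², that is 94, 135 and 184 per agent. By Table 2's own method, 510 patients would detect about 0.31.

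**5. Does the omnibus reading rescue 292?** If only DTG is shifted by 0.41, λ = 292 × 0.16 × (0.41/SD)². Power on 4 df is 59%, 42% and 32% at SD 1.0, 1.2 and 1.4.

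**6. Does allocation rescue 292?** With four comparators, the weakest contrast is best served when DTG is twice the size of each comparator, about 97 against 49. At SD 1, power per contrast is then about 64%. So at SD 1 or above, no allocation of 292 gives 80% for every DTG contrast.

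**7. Larger strata.** Pairwise detectable differences at SD 1.0, 1.2 and 1.4, against Table 2's method:

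| Stratum | SD 1.0 | SD 1.2 | SD 1.4 | Table 2 method |
|---|---|---|---|---|
| Normal weight (6,598) | 0.11 | 0.13 | 0.15 | 0.085 |
| Overweight (6,298) | 0.11 | 0.13 | 0.16 | 0.087 |
| Obese (3,964) | 0.14 | 0.17 | 0.20 | 0.11 |

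**The case against.** The protocol states its 4-df basis openly, and this is an analysis of an existing database. No recruitment, endpoint or model depends on Table 2, and the estimates would be the same without it. That stands, and it limits the harm to how results are interpreted.

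The 292 figure is an illustration, not a stratum. The relevant comparison is 510, where power is better and passes 80% at SD 1 with equal groups. That also stands. The three other strata hold 16,860 of the 17,370 patients and are well powered for 0.4 under an equal split.

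The SDs are uncertain. They are back-calculated from two-decimal standard errors in one cohort, are not specific to underweight patients, and straddle 1 at 6 months. They are also unadjusted, so the residual SD in the planned model could be smaller. This is why a range is shown. It does not justify an unstated value of 1.

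Two stronger readings are tempting, and the documents support neither.

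- A reader might infer that the figure is wrong for every DTG contrast. Agent shares are not given. If DTG and one comparator made up 40% and 35% of the 292, power at SD 1 would be about 85%. Two groups of 146 would give 94% at SD 1 and 83% at SD 1.2.
- A reader might infer that the protocol contradicts itself by pleading "due to the lack of published data on the relationship between the core agents of interest in this study and BMI" after reporting such data in section 6.1. That reason is given for not using the R² method, which needs expected R² values, and section 6.1 reports none. The SD is mentioned separately, as a drawback of the ANOVA alternative.

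**Conclusion.** The point holds as a wrong stated figure. The Table 2 differences are in BMI units only if the residual SD is 1, and even then they do not belong with 4-df sample sizes when the question is DTG against each other agent. At SD 1 or above, 292 patients cannot give 80% power for all DTG contrasts of 0.41.

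The practical effect falls on the underweight stratum. With equal groups and SDs of 1.2 to 1.4, power there for 0.41 is about 68% to 55%, so the reassurance drawn from 510 exceeding 292 fails. The 510 is a baseline count, and section 8.5 restricts each analysis to patients followed to the time point, so the analysed number can only be equal or smaller. For the larger strata, the conclusion that 0.4 is detectable survives under an equal split. Only the implied detectable differences are too small.

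These results assume alpha 0.05 two-sided, five equal groups except where stated, and ± read as a standard error. Unequal shares could raise power for a contrast between two large groups, and would lower it for a contrast with a small one.

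**What to change.** Do one of the following in section 8.5.3:

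- relabel the Table 2 column as a standardised difference (SD units), tied to the omnibus test; or
- recompute detectable BMI differences for 1-df DTG-versus-comparator contrasts, with a stated SD of BMI change (for example a range of 1.0 to 1.5, since section 6.1 implies about 1.2 at 6 months and 1.4 at 12 months) and the expected number of patients per agent in each stratum.

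In either case, withdraw or qualify the 292-patient sentence, and state that the underweight stratum may not be powered for pairwise differences of about 0.4 BMI units.

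The cost is one revised table and two sentences, with less favourable stated figures. The second option also needs agent counts per stratum from the database. The cohort and the analysis model do not change.

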8.5. Data analysis

For each time point assessed (6,12, or 24 months), the study population will be restricted to patients with a follow-up greater or equal to that time point.

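### Section 8.5.3 has the effect of censoring weights on sample size the wrong way round and compares Table 2 with baseline counts, so the margin is overstated, mainly in the underweight stratum

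*Protocol*

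**What the plan says.** Section 8.5.3 gives the N required "with 80% power for the adjusted linear regression" over a range of partial correlations. The exposure is a five-level variable, "which is equivalent to 4 factor variables, thus requiring 4 degrees of freedom", and the section adds: "Calculations were performed assuming a total of 10 covariates included in the model in addition to the exposure variables". Table 2 runs from 29,832 patients (difference 0.04) to 292 patients (difference 0.41).

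Below Figure 2 the section says that these sizes "are likely a overestimation of the sample size required when inverse probability of censoring weights are included". It then offers reassurance that small differences remain detectable in much smaller samples. Its one example sets the 292 against the observation that "the smallest stratum available in OPERA is the underweight group, with 510 patients".

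The available numbers are described in the same section: "17,370 were ART-experienced, had a baseline BMI and initiated one of the core agents of interest for the first time" within the inclusion period. They divide into 510 underweight, 6,598 normal weight, 6,298 overweight and 3,964 obese.

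Other sections define a narrower analysed set. Section 8.5 says that at each time point "the study population will be restricted to patients with a follow-up greater or equal to that time point". Section 8.1 censors at core agent discontinuation, loss of clinical activity, pregnancy, death and 31DEC2018. Section 8.3.2 requires a BMI inside a window around each time point. Section 8.5.1 applies censoring weights and stratifies the BMI model by baseline BMI category.

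**The concern.** Two statements err in the same direction.

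First, inverse-probability-of-censoring weights let patients who remain stand in for those who were censored. The weighted total may look like the original cohort, but no information is added. Under the constant-variance linear model behind Table 2, unweighted least squares is already the most precise linear unbiased estimator, so unequal weights can only cost precision.

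Second, 510 is the N of an underweight outcome model only if nobody is lost, censored or left without a BMI in the window.

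The study is meant to support a safety signal evaluation (Section 6.2), and the BMI model is stratified. A 24-month underweight result showing no difference could be read against a sensitivity that the analysed data do not have.

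**Working it through.** **Inputs from the protocol.** Power 80%; 4 tested degrees of freedom; 10 further covariates, so 14 predictors; ρ = d/√(d²+4); stratum counts as above; inclusion 01AUG2013 to 31DEC2017; observation to 31DEC2018.

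**Inputs assumed.** α = 0.05 (not stated), even accrual, retention, and variability of the weights. The protocol gives no figure for any of these, so ranges are shown. Differences are on the plan's own scale, which its conversion formula ties to an SD of 1.

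**1. Reproduce Table 2.** Overall F test with 4 and N−15 degrees of freedom and noncentrality λ = Nρ²/(1−ρ²). For ρ = 0.20:
- d = 2×0.20/√(1−0.04) = 0.41
- λ at N = 292 is 292×0.04/0.96 = 12.17
- power is 0.7994 at N = 291 and 0.8009 at N = 292

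All ten rows match exactly. The calculation contains no term for weights or attrition.

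**2. Direction of the weighting effect.** Required N becomes about N×(1+CV²).
- CV 0.5 (assumed): 1+0.25 = 1.25, and 292×1.25 = 365
- CV 0.75 (assumed): 1+0.5625 = 1.56, and 292×1.56 ≈ 456

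In a simulated regression among completers, with about 54% retained, weighted-to-unweighted variance ratios were 1.02, 1.08 and 1.24. The 1+CV² values were 1.02, 1.08 and 1.27. The required N rises in every case.

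**3. Calendar limit at 24 months.** An index date after 31DEC2016 cannot give 24 months of follow-up by 31DEC2018. This affects 365 of 1,614 inclusion days, 22.6%. With even accrual, 510×0.774 ≈ 395. At 12 months the last starter can still just reach the time point, so only the 24-month analysis loses patients to the calendar alone.

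**4. Break-even.** For 80% power at 0.41, retained share divided by design effect must be at least 292/510 = 0.57 of the baseline count. Starting from the 395, that means retaining 292/395 = 74% without weighting loss, or 365/395 = 92% at a design effect of 1.25.

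**5. Underweight stratum at 24 months.** Power is at d = 0.41; the detectable difference is at 80% power. With the full 510 these are 0.97 and 0.31.

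| Share of the 395 remaining (assumed) | N | Power, no weighting loss | Detectable difference | Power, design effect 1.25 | Detectable difference |
|---|---|---|---|---|---|
| 100% | 395 | 0.92 | 0.35 | 0.84 | 0.39 |
| 80% | 316 | 0.84 | 0.39 | 0.73 | 0.44 |
| 70% | 276 | 0.78 | 0.42 | 0.66 | 0.47 |
| 60% | 237 | 0.70 | 0.45 | 0.59 | 0.51 |
| 50% | 197 | 0.61 | 0.50 | 0.50 | 0.56 |

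**6. Other strata.** Take 50% of those able to reach 24 months and a design effect of 1.56. For example, 3,964×0.774×0.5/1.56 ≈ 980 and 6,598×0.774×0.5/1.56 ≈ 1,640. The detectable difference is then 0.17 to 0.22 and power at 0.41 exceeds 0.99.

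**The case against.** The strongest reply is that the sentence is a one-word slip. The next sentence opens with a contrast and offers reassurance about smaller samples, which makes sense only if an underestimate was meant. That is probably right, but the text as it stands says the opposite and needs correcting.

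It can also be said that the protocol labels its counts openly as baseline counts and notes that much smaller samples would do. This stands in part. However, no follow-up count is given, and the only worked example is 510 against 292, the comparison most exposed to attrition.

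Finally, this is a fixed cohort using all eligible patients, so no recruitment target or estimate changes. That stands, and it limits the consequence to how the results will be read.

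A reader might infer several stronger things that the protocol does not support:
- That its conclusion relies on a gain from weighting. The 292 contains no weighting term and no reduction is taken anywhere.
- That it claims a given power in each stratum. It states none; only the margin of available over required N is overstated.
- That the underweight analysis is shown to be too small. The calendar limit alone leaves about 395, still above 292. Falling below depends on assumed retention or weight variability.
- That the loss should be expressed as a pairwise difference with a larger SD. That changes the test and the scale, and most of the resulting gap would come from those changes.

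**Conclusion.** The concern holds in this form: Section 8.5.3 states the wrong direction for the effect of censoring weights, and it compares Table 2 with counts that are not those of the outcome models. Neither part depends on an assumed retention rate, and nor does the exclusion of 2017 starters at 24 months.

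The size of the loss does depend on assumptions. With even accrual and 50 to 70% of the 395 remaining, the 24-month underweight stratum has power of about 0.61 to 0.78 at 0.41 and a detectable difference of 0.50 to 0.42. Both are worse with a design effect above 1. The practical effect is mainly in that stratum, 510 of 17,370 patients (2.9%). Table 2 itself is computed correctly on its stated inputs with α = 0.05.

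**What to change.** In Section 8.5.3:
- Change *overestimation* to *underestimation*, and state that the required N is to be multiplied by the weighting design effect 1+CV², with the CV assumed.
- Restate the available N for each baseline BMI stratum at 6, 12 and 24 months, counting patients with follow-up on the agent to that point and a BMI in the window. For 24 months, include only index dates that allow 24 months of follow-up by 31DEC2018.
- Divide these counts by the design effect, compare the results with Table 2, and replace the 510-against-292 example accordingly.

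The cost is one count query on the existing database and a few revised sentences. The stated figures will look less favourable, chiefly for underweight patients at 24 months.
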